12.2 Medical treatment and protection of subjects during the study (if any) .....	28
12.3 Medical and protection after study procedure (if any) .....	29
13. Supporting documentation and precautions .....	38
13.1 Informed consent process (if any) .....	43
13.2 Privacy Protection (must) .....	43
13.3 Collection and use of Specimens and Data (necessary) .....	34
13.4 Quality Control and Quality Assurance (necessary) .....	46
13.5 Data processing and record keeping (necessary) .....	46
13.5.1 Data collection and management .....	46
13.5.2, and the study data were retained .....	46
13.6 Publication and Data Sharing Agreements (if any) .....	36
13.7 Conflict of interest statement (must) .....	48
14. References (must) .....	48

scenario summary	
Research name	A Phase II clinical study of calbenizimumab (AK 104) plus chemotherapy for PD-1 inhibitor-resistant nasopharyngeal carcinoma
Research profile	
AK 104 is a humanized immunoglobulin G1 (IgG 1) bispecific antibody (BsAb) with crystallizable fragment (Fc) mutations to eliminate the Fc-receptor and complement-mediated cytotoxic effects. AK 104 is able to bind both programmed cell death receptor-1 (PD-1) and cytotoxic T lymphocyte-associated antigen-4 (CTLA-4) and block the interaction of PD-1 / programmed cell death ligand-1 (PD-L1), PD-1 / PD-L2, CTLA-4 / B7.1, and CTLA-4 / B7.2.
 
AK 104 is a tetravalent IgG-ScFv bispecific antibody. AK 104 contains a point mutation in its constant region that prevents the binding of the complement protein C1q and the Fc <math>\gamma</math> receptor involved in the cytotoxic effect. AK 104 is expressed in a Chinese hamster ovary cell line with a total molecular weight including oligosaccharides of about 200 kDa.

purpose of research	
fundamental purpose
 
 
• To evaluate the safety and efficacy of calbenizimumab plus chemotherapy (platinum-based) second-line treatment of PD-1 inhibitor-resistant NPC based on RECIST v 1.1 Objective response rate (ORR) and PFS as assessed.
 
 
Secondary purpose

	
 
• To evaluate DoR, DCR, TTR, TTP, and OS in PD-1 inhibitor-resistant NPC with capradilimumab plus chemotherapy (platinum-based).
 
• To evaluate the pharmacokinetics of carradilizumab plus chemotherapy (Pharmacokinetics, PK).
 
• To assess the immunogenicity of calradilizumab in combination with chemotherapy.
 
• To evaluate the correlation of PD-L1 expression with efficacy in immunohistochemical detection of tumor samples.
 
• To evaluate the association of EB virus (EBV) DNA copy number in blood and antitumor activity of caadilimumab in subjects with advanced NPC.
 
 
To assess health-related quality of life (HRQoL) in subjects treated with carradiniilizumab plus chemotherapy

research design	
This study is a Phase II clinical study of carradilimumab (AK 104) plus chemotherapy for PD-1 inhibitor-resistant nasopharyngeal cancer to evaluate the safety and efficacy of carradilimumab plus chemotherapy as second-line and above treatment for PD-1 inhibitor-resistant nasopharyngeal cancer.
 
This study is a single-arm, phase II clinical study with approximately 30 PD-1 inhibitor-resistant NPC subjects scheduled to be enrolled. PD-L1 CPS (<50% vs > 50%, subjects whose PD-L1 expression was not evaluated were classified as <50%) were used as the stratification factor. The study will have a safe lead-in period of approximately 6 PD-1 inhibitor-resistant subjects, and the investigator will conduct an preliminary safety assessment. If the safety and

	
tolerance are good and initial efficacy signals are observed, the extended enrollment phase will enter. Efficacy analysis will be performed for approximately 15 subjects. If 6 of the 15 subjects are not tolerated, subject enrollment may be stopped after the investigator discussion. After poor safety, the investigator decided to revise or stop the study. For 4-6 cycles, the use of caldulizumab until the investigator determines that there is no clinical benefit (based on the comprehensive judgment of RECISTv1.1 imaging assessment and clinical symptoms), toxicity intolerance, completion of 24 months of treatment, or satisfaction of other criteria for treatment termination in the regimen, whichever occurs first.
 
 
• Subject treatment protocol:
 
• Caradilizumab (200 mg, administered on Day 1, Q3W until no longer clinical benefit) + platinum-based chemotherapy, Q3W, 4-6 cycles), treatment cycle every 3 weeks (21 days).
 

Total number of enrolled patients	30 Cases
Number of research groups Number of control groups	The number of the study group was 30 cases
diagnose	nasopharyngeal darcinoma
Selection criteria	
Selection criteria:
 
Subjects must meet all of the following inclusion criteria to be enrolled in the study:

[figure not shown]
	
Voluntary signed the written ICF.
 
 
1) Age was over 18 and 75 at the time of enrollment, acceptable for both men and women.
 
2) The Eastern Cooperative Oncology (ECOG) physical performance score was 0 or 1.
 
3) Expected survival is greater than 3 months.
 
4) Histologically or cytologically confirmed nasopharyngeal carcinoma.
 
5) The subject had previously failed treatment with PD-1 inhibitor and had no indication for radical local treatment.
 
6) According to the efficacy evaluation criteria of solid tumors RECIST v 1.1 with at least one measurable lesion.
 

Exclusion criteria	
Research intervention	
This study is a Phase II clinical study of carradilimumab (AK 104) plus chemotherapy for PD-1 inhibitor-resistant nasopharyngeal cancer to evaluate the safety and efficacy of carradilimumab plus chemotherapy as second-line and above treatment for PD-1 inhibitor-resistant nasopharyngeal cancer. AK 104 has been approved for marketing and is not approved for nasopharyngeal cancer. The reasons for this study intervention in NPC are as follows: 1. Clinically, more and more NPC patients develop PD-1 inhibitor resistance. 2. A large amount of research evidence shows that the combination of PD-1 antibody and CTLA-4 antibody avoids the dark side of PD-1 antibody to some extent and effectively reduces the occurrence of PD-1 inhibitor resistance in

	
tumors. PD-1 and CTLA-4 complement each other and do not repeat in regulating immune responses, with mechanisms preventing T cell depletion and promoting T cell activation, respectively. When the PD-1 pathway and CTLA-4 modulation target the two pathways (Pardoll, 2012), they have more effective anti-tumor activity than single-agent therapy.

evaluation criterion:
 
Main end point:
 
Secondary end point:
 
safety evaluation:
	
Main end point
 
Safety: Incidence and severity of adverse events (AEs), clinically significant abnormal laboratory findings.
 
Based on the following data in RECIST v i. The ORR as assessed by the I.
 
Based on the following data in RECIST v i. I of the assessed PFS.
 
Secondary end point
 
According to the RECIST vi. The DoR, DCR, TTR, TTP, and OS as assessed by I.
 
PK characteristics: including serum concentrations of caadalinilimumab at different time points after caadabinibizumab administration.
 
Immunogenicity assessment: Number and percentage of subjects presenting with detectable antimicrobial antibodies (ADA).
 
To evaluate the correlation of PD-L1 expression with efficacy in immunohistochemical detection of tumor samples.
 
To evaluate the association of EB virus (EBV) DNA copy number in blood and antitumor activity of caadilimumab in subjects with advanced NPC.

	Health-related Quality of Life Assessment HRQoL-as measured using the European Organization for Research and Treatment of Cancer Quality of Life Questionnaire-Core 30 (EORTCQLQ-C30) and EORTCQLQ-H & N35.
statistical method:	
sample capacity:	A total of 30 subjects are planned to be enrolled as a single-arm, phase II clinical study. This study used historical data as a control with no formal statistical hypothesis.
analytic set:	efficiency analysis
Primary	The primary study endpoint of this study was according to the RECIST v 1.1. And 1 the ORR and PFS assessed.
Efficacy Endpoint:	
Safety end:	Analysis of the primary endpoint was performed after the last subject who met the statistical and imaging assessment requirements had completed at least 24 weeks of follow-up (or disease progression). The ORR and OCR analyses will be performed based on the full analysis set, with their 95% exact two-sided confidence intervals estimated by the Clopper Pearson method. The time to reach the event endpoint (OOR, PFS, and OS) was analyzed by the Kaplan-Meier method. The PFS and OS analyses will be performed based on the randomized analysis set. The graphical analysis will include a spider map of the percent change in target lesion tumor load from baseline over time, and a waterfall plot of the best percentage of change in target lesion tumor load from baseline.
	safety
	The safety analysis will be based on the safety analysis set, which includes all enrolled subjects who have received any study drug. Summary statistics for AEs will be summarized for all adverse events, adverse events related to study drug,

	serious adverse events (SAEs) and for AEs and AESIs leading to discontinuation. Will be based to the National Cancer Institute Common Terminology Criteria for Adverse Events (National Cancer Institute Common Terminology Criteria for Adverse Events, NCI CTCAE) Version 5.0 grades the AEs, And adopt the International Medical Dictionary for Regulatory Activities (Medical Dictionary for Regulatory Activities, Med DRA) For encoding. Laboratory abnormal findings and toxicity levels will be summarized per version NCI CTCAE 5.0. In the cross table of clinical laboratory examinations, the change in baseline CTCAE grade and highest-severity grade after baseline will be shown and grade CTCAE 3 or 4 clinical laboratory abnormalities will be listed.
Study duration	Three years
Participation time of the subjects	Three years
Study unit / site	Department of Head and Neck Oncology, Cancer Center, Union Hospital, Huazhong University of Science and Technology
Principal Investigator Data	

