According to the report, NPC is closely associated with EB virus infection, and the tumor has high expression of PDL 1, suggesting that PDI blockade is an ideal treatment option for NPC. PD-1 is a negative immunomodulator molecule that mediates tumor immunosuppression in the local tumor microenvironment. The KEYNOTE-028 phase Ib study (NCT 02054806) evaluated the clinical efficacy of the immune checkpoint blockade agent pembrolizumab in the treatment of recurrent / metastatic NPC. Twenty-seven patients with recurrent / metastatic NPC with positive PD-L1 expression receiving 10mg / kg pembrolizumab once every 2 weeks achieved an ORR of 25.9% by investigator assessment, a median response duration of 17.1 months, and one additional unconfirmed partial response. Five of the confirmed partial responses (26.3%) in 19 subjects assessed by the Independent Imaging Evaluation Committee (IRRC). Pembrolizumab The median overall survival for the

treatment of recurrent / metastatic NPC was 16.5 months, and the overall 1-year survival rate was 63%. In some other cytotoxic and noncytotoxic drug studies, overall 1-year survival is reported at around 45%.

Another phase II study (NCT02339558) evaluated the clinical efficacy of the immune checkpoint blocker nivolumab in the treatment of recurrent / metastatic NPC.44 patients with recurrent / metastatic NPC treated with 3mg / kg nivolumab every 2 weeks achieved ORR of 20.5% by investigator assessment, median remission continuation of 9.3 months, median overall survival of 17.1 months and overall 1-year survival rate of 59%. ORR reached 33% in 18 PD-L1 positive patients; in 23 PD-L1 negative cases. This shows that the application of PD-1 inhibitors in NPC patients has a solid theoretical basis and sufficient practical basis as a support. However, with the gradual and widespread application of PD-1 inhibitors in clinical practice, PD-1 inhibitor resistance has also become another therapeutic challenge.

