#### **1.4.2 Known potential benefits**

As a population resistant to PD-1 inhibitors, only chemotherapy is used clinically, and the effective rate is less than 20%. If combined with A K104 and chemotherapy, patients are highly likely to obtain the most effective treatment from this combination treatment.

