## **3. research design**

### **3.1 Overall design (must)**

This study is a Phase II clinical study of carradilimumab (AK 104) plus chemotherapy for PD-1 inhibitor-resistant nasopharyngeal cancer to evaluate the safety and efficacy of carradilimumab plus chemotherapy as second-line and above treatment for PD-1 inhibitor-resistant nasopharyngeal cancer. This study is a single-arm, phase II clinical study with approximately 30 PD-1 inhibitor-resistant NPC subjects scheduled to be enrolled. PD-L1 CPS (<50% vs > 50%, subjects whose PD-L1 expression was not evaluated were classified as <50%) were used as the stratification factor. The study will have a safe lead-in period of approximately 6 PD-1 inhibitor-resistant subjects, and the investigator will conduct an preliminary safety assessment. If the safety and tolerance are good and initial efficacy signals are observed, the extended enrollment phase will enter. Efficacy analysis will be performed for approximately 15 subjects. If 6 of the 15 subjects are not tolerated,

subject enrollment may be stopped after the investigator discussion. After poor safety, the investigator decided to revise or stop the study. For 4-6 cycles, the use of calduilizumab until the investigator determines that there is no clinical benefit (based on the comprehensive judgment of RECISTv1.1 imaging assessment and clinical symptoms), toxicity intolerance, completion of 24 months of treatment, or satisfaction of other criteria for treatment termination in the regimen, whichever occurs first.

- Subject treatment protocol:
- Carradilizumab (200 mg, administered on day 1 of each cycle, Q3W until no longer had clinical benefit) + platinum was based chemotherapy, 1 treatment cycle every 3 weeks (21 days).

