### **3.2 Sample size (necessary)**

Thirty subjects are planned to be enrolled in this study

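### Must the protocol fix a historical response rate and a response cut-off for the efficacy look at about 15 subjects?

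*Protocol*

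**What the plan says.** The sample capacity row of the scenario summary plans 30 subjects in a single arm and adds: "This study used historical data as a control with no formal statistical hypothesis". Section 3.2 says only "Thirty subjects are planned to be enrolled in this study". Section 1.2 calls the study exploratory.

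Response rates in nasopharyngeal carcinoma appear elsewhere, but none is tied to the control:

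- Section 1.4.2, on patients resistant to PD-1 inhibitors: "only chemotherapy is used clinically, and the effective rate is less than 20"%. It is an upper bound and has no citation.
- Section 1.3, on PD-1 inhibitors in recurrent or metastatic disease: the nivolumab study "achieved ORR of 20.5% by investigator assessment" and the pembrolizumab study "achieved an ORR of 25.9% by investigator assessment". Neither group is described as PD-1 resistant.

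On looks during enrolment, Section 3.1 has a lead-in of about 6 subjects, after which "If the safety and tolerance are good and initial efficacy signals are observed, the extended enrollment phase will enter". Next comes, in the words of the scenario summary, "Efficacy analysis will be performed for approximately 15 subjects. If 6 of the 15 subjects are not tolerated, subject enrollment may be stopped", and then a sentence on poor safety. The efficacy part of the summary times the main analysis: "Analysis of the primary endpoint was performed after the last subject who met the statistical and imaging assessment requirements" had been followed for at least 24 weeks or had progressed. ORR is reported with a Clopper-Pearson 95% interval and PFS by Kaplan-Meier.

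**The concern.** In a single-arm trial the historical rate is the only comparator. If it is left open until the data are in, it can be chosen to suit them. A final 10/30, for instance, has an interval of 17.3% to 52.8%, which lies above 15% but not above 20%.

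The 15-subject look also seems lopsided. Tolerability has a count and efficacy has none, although the look is called an efficacy analysis. Even 0/15 is linked to no review of enrolment, and the earlier efficacy condition after about 6 subjects carries no number. At stake would be how the primary ORR is read, and whether up to half the planned sample is enrolled on a regimen showing little activity.

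**Working it through.** **Can the planned size be reproduced?** No. The protocol states no null rate, target rate, error rate, power or precision goal, so 30 is a declared choice and there is no derived figure to check.

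**Inputs.** n = 30 and n of about 15 come from the scenario summary and Section 3.1. The reference of 20% is the bound in Section 1.4.2, taken at its limit. 20.5% and 25.9% come from Section 1.3. References of 10% and 15%, and true ORRs of 10% to 40%, are assumptions.

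**Step 1: does the reference enter any planned result?** The Clopper-Pearson lower limit p_L solves P(X ≥ x | n, p_L) = 0.025, and the upper limit p_U solves P(X ≤ x | n, p_U) = 0.025. Only x and n enter. The Kaplan-Meier estimate of PFS uses no external rate either. Every planned output is the same whichever reference a reader has in mind.

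**Step 2: how far does the reading move?** The interval excludes p0 from below at the smallest x with P(X ≥ x | 30, p0) < 0.025.

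| p0 | Origin | Tail at the count below | First count clear of p0 |
|---|---|---|---|
| 20% | Section 1.4.2 bound | P(X ≥ 11) = 0.0256 | 12/30, tail 0.0095 |
| 20.5% | Section 1.3 | P(X ≥ 11) = 0.0303 | 12/30, tail 0.0116 |
| 25.9% | Section 1.3 | P(X ≥ 13) = 0.0286 | 14/30, tail 0.0113 |
| 15% | assumed | P(X ≥ 9) = 0.0278 | 10/30, tail 0.0097 |

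An assumed 10% would give 8/30. The bound for this population and the nivolumab figure lead to the same count, 12/30 (interval 22.7% to 59.4%). The lower counts need values that the protocol does not state, and the higher one needs a rate from a different population. The exercise also treats the interval as a pass/fail test, which the protocol disclaims.

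**Step 3: what could the 15-subject look tell anyone?** With no responders the upper limit is 1 − 0.025^(1/15) = 21.8%. With 2/15 the interval is 1.7% to 40.5%, which covers both an inactive and a useful regimen.

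Take a guide of 2/15 or fewer as an illustration. The probability of a review is P(X ≤ 2) = (1−p)^15 + 15p(1−p)^14 + 105p²(1−p)^13.

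- p = 20%: 0.0352 + 0.1319 + 0.2309 = 0.398
- p = 40%: 0.0005 + 0.0047 + 0.0219 = 0.027
- p = 10%: 0.816; p = 15%: 0.604; p = 35%: 0.062

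At 20%, the limit of the only bound given for these patients, such a guide would stay silent in 1 − 0.398 = 60% of cases. It is also sensitive to the planned approximation of 15: at 20% the probability is 45% with 14 subjects and 35% with 16, and at 35% it is 8.4% and 4.5%.

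**Step 4: does the text block action on poor efficacy?** It does not. Nothing in Section 3.1 prevents the investigator from halting enrolment after a poor efficacy result. An efficacy condition applies before expansion, and an individual's treatment ends when the investigator sees no clinical benefit.

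**The case for a change.** The strongest reply is that this is more than missing detail. The protocol itself invokes a control and schedules an efficacy look, so it should say what the control is and what the look is for. Naming a comparator in advance guards against picking one afterwards, even when the comparison is descriptive. A bound of under 20% is not a value. Whether enrolment continues is trial conduct, which the protocol already governs for tolerability. The remedy would be two sentences, with no extra subjects and no test.

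Much of this stands as fact. The 20% bound is uncited and is not linked to the control. PFS, also a primary endpoint under the same statement, has no historical figure at all. The look has no written efficacy consequence.

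What does not stand is the weight. The source of a descriptive comparator is a detail that a statistical analysis plan can hold, and that document may exist unseen. An exploratory single-arm study need not carry a futility rule. A non-binding review with the cut-off left for the sponsor to choose would add little to the discretion already available. Savings in subjects, such as 15 × 0.398 = 6.0 on average at a true ORR of 20%, arise only if every review stops accrual at once, which a non-binding guide does not imply.

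**Conclusion.** No change to the plan follows. The observations are accurate, but no estimate, interval or stated figure is wrong, and no planned output depends on the missing reference. With the only bound given for this population taken at 20%, the exact interval clears it from 12/30, and 20.5% gives the same count. Wider spreads rest on assumed references or on patients not described as PD-1 resistant. A response guide at 15 subjects would be optional. With 2/15 as the illustration, it would prompt a review 40% of the time at a true ORR of 20% and 2.7% at 40%.

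This rests on 30 subjects in the full analysis set, on the true rates assumed above, and on the study being reported as exploratory with no claim of superiority over history. A later report that does claim superiority would need a sourced reference for ORR and one for PFS. Citing the Section 1.4.2 figure and linking it to the control would be a helpful clarification, but it is not a correction.

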## Flow chart of the study

## Acronym table

abbreviation	The full text of Chinese
AASLD	, The American Society for the Study of Liver Diseases
ADA	Anti-drug antibodies
AE	adverse event
AESI	Adverse events, and of special interest
ALP	alkaline phosphatase
ALT	glutamic-pyruvic transaminase
ANC	Absolute neutrophil count
AST	glutamic-oxalacetic transaminase
AUC	Area under the concentration-time curve
BCLC	The Barcelona liver cancer clinical staging system
CI	confidence interval
CL	clearance
CNS	C. N. S
CR	complete remission
CRA	Clinical study monitor
CRO	contract research organization
CrCl	CC
CT	computerized tomographic scanning
DCR	Disease control rate
DLT	dose-limiting toxicity

dMMR	Mismatch repair-defective type
DoR	Relieve duration
ECG	electrocardiogram
ECOG	The Eastern US Cooperative Oncology Group
eCRF	Electronic case report form
EDC	Electronic data acquisition
EFS	Event-free survival
Fc	FC
FDA	The US Food and Drug Administration
FFPE	Formalin was fixed fixed and embedded in paraffin wax
GCP	Practice management of drug clinical trials
GLP	Good Laboratory Practice for Drug Non-clinical Studies
HBV	HBV
HCC	hepatocellular carcinoma
HCV	hepatitis C virus
HIV	human immunodeficiency virus
ICF	informed consent
ICH	International Conference on coordination requirements for human medicines
IEC	Independent ethics committee
Ig	immunoglobulin
IgG1	Immunoglobulin G1
IHC	immunohistochemistry
irAE	Immune-related adverse events
IRB	The Institutional Review Board
IV	I.V
IVIG	Intravenous immunoglobulin was administered
LFT	liver function test

LLN	lower limits of normal
mAb	monoclonal antibody
MedDRA	The International Medical Dictionary for Regulatory Activities
MRI	nuclear magnetic resonance
MSI-H	Height microsatellite instability type
NCI CTCAE	US National Cancer Institute Common Terminology Criteria for Adverse Events
NHC	The National Health and Family Planning Commission of the People's Republic of China
NMPA	The National Medical Products Administration
NSAID	non-steroid anti-inflammatory drug
NSCLC	nonsmall-cell lung cancer
ORR	Objective mitigation rate
OS	Overall survival
PD	PD
PD-1	Programmed cell death-1
PD-L1	Promed cell death ligand-1
PD-L2	Promed cell death ligand-2
PFS	Progression-free survival
PK	pharmacokinetics
PR	partial remission
Q2W	Once every 2 weeks
QTcB	QT interval corrected by heart rate using the Bazett formula
QTcF	QT interval corrected by heart rate using the Fridericia formula
RECIST	Criteria for efficacy evaluation in solid tumors
RO	Receptor share
SAE	Serious adverse events
SAP	Statistical analysis plan
SD	stable disease

SID	Subjects number
t 1/2	half-life period
TTR	To ease the time
TBil	total bilirubin
TIL	TIL
TSH	TSH
ULN	Upper limit of normal value
WHO-DD	The World Health Organization Dictionary of Drugs

